## 7.2. Handling of missing data

### 7.2.1. Demography

For a given subject and a given demographic variable, missing measurement will not be replaced except for age.

### 7.2.2. Reactogenicity and safety

For a given subject and a given measurement, missing or non-evaluable measurements will not be imputed. The missing endpoint and censoring are supposed to occur independently, and the pattern of the missing value(s) being either Missing Completely At Random (MCAR) or Missing At Random (MAR) only.

For the analysis of solicited symptoms, missing or non-evaluable measurements will not be replaced. Therefore the analysis of the solicited symptoms based on the TVC will include only subjects/doses with documented safety data (i.e., symptom screen/sheet completed).

For the analysis of unsolicited symptoms/SAEs/pIMDs/concomitant medication, all vaccinated subjects will be considered and subjects who did not report an event will be considered as subjects without an event.

# Statistical Analysis Plan

GlaxoSmithKline

Study alias & e-track number(s): ZOSTER-063 (204928)

## 7.2.2.1. **Solicited general symptoms**

The analysis of solicited general symptoms will include all subjects for whom the question (1) in [Figure 2](#) about the presence of any solicited general symptom has been answered by 'Yes' or 'No' (see the GENSOL\_YN item).

The next sections describe how each subject contributes to the analyses, depending on the endpoints.

# Statistical Analysis Plan

Study alias & e-track number(s): ZOSTER-063 (204928)

**Figure 2** Information captured in the clinical database for solicited general symptoms

**ZOSTER-063 (204928): SOLICITED SYMPTOMS (Solicited symptoms)**

**SOLICITED ADVERSE EVENTS - GENERAL SIGNS/SYMPOTMS - TEMPERATURES - REACTOGENICITY TRIGGERED MEDICAL ATTENTION**

2.\* Has the subject experienced any of the General Solicited signs/symptoms between Day 0 and Day 6?

**1**

[GENSOL\_YN]  
[A:Y]  Yes -> Please:  
  
• tick No/Yes for each sign/symptom and complete further as necessary in the "General signs/symptoms (except temperature)" form,  
• complete "Temperatures" and "Reactogenicity triggered medical attention" forms.  
[A:N]  No -> Please complete the "Temperatures" form  
[A:U]  Unknown, no information available

Key: [\*] = Item is required  
Note: Hidden items are not displayed.  
Note: Source verification critical settings made in InForm will override any settings made in Central Designer.

**ZOSTER-063 (204928): SOLICITED ADVERSE EVENTS - GENERAL SIGNS/SYMPOTMS (EXCEPT TEMPERATURE) (General signs/symptoms (except temperature))**

If any of these adverse events meets the definition of serious, complete an Expedited Adverse Event Report.

**HEADACHE**

1.\* Occurred?

**2**

[HE\_YN]  
[A:N]  No  
[A:Y]  [SYMP\_VAL\_INTEN]  
Yes -> [SYMP\_VAL\_INTEN\_D0] [SYMP\_VAL\_INTEN\_D1] [SYMP\_VAL\_INTEN\_D2] [SYMP\_VAL\_INTEN\_D3] [SYMP\_VAL\_INTEN\_D4] [SYMP\_VAL\_INTEN\_D5] [SYMP\_VAL\_INTEN\_D6]  
Intensity: Day 0: [INTENSITYSOL] Day 1: [INTENSITYSOL] Day 2: [INTENSITYSOL] Day 3: [INTENSITYSOL] Day 4: [INTENSITYSOL] Day 5: [INTENSITYSOL] Day 6: [INTENSITYSOL]  
[SYMP\_TM]  
Symptom first onset time: [Req/Unk] : [Req/Unk] 24-hour clock  
[HE\_ONG]  
After Day 6: Ongoing? [A:N]  No  
[A:Y]  [SYMP\_ONG\_INTEN]  
Yes -> [SYMP\_MAX\_INTEN]  
Maximum intensity: [INTENSITYSOLMAX]  
[ERDAT]  
Date of last day of sign/symptom: [Req/Unk] / [Req/Unk] / [Req/Unk] (2016-2018)  
[CONT\_END]  
Continuing at the end of the study? [A:Y]   
[CAUSAL]  
Is there a reasonable possibility that the AE may have been caused by the investigational product? [A:Y]  Yes  
[A:N]  No

# Statistical Analysis Plan

GlaxoSmithKline

Study alias & e-track number(s): ZOSTER-063 (204928)

For each solicited general symptom if the answer to (2) in [Figure 2](#) is "No", the subject will be considered as not having that symptom after that dose.

**Subjects who documented the presence of a specific symptom** i.e., if the answer to (2) in [Figure 2](#) is "Yes" (ex FA\_YN=Y), the maximum intensity recording over the considered follow-up period is used for the analysis of the percentage of subjects with symptoms.

**If the subject answered "Yes" to (2) in [Figure 2](#) for a specific symptom BUT partially recorded daily measurement** (e.g. intensity missing for Day 3) over the considered solicited period, s/he will be included in the summaries and classified according to their maximum observed daily recording over the solicited period.

**If the subject answered "Yes" to (2) in [Figure 2](#) for a specific symptom BUT no daily measurement is recorded**, s/he will not be included and counted in the summary of subjects with symptoms above a specified threshold, however s/he will be part of the summary corresponding to the 'All' category.

# Statistical Analysis Plan

Study alias & e-track number(s): ZOSTER-063 (204928)

## 7.2.2.2. Solicited general fever

Figure 3 Information captured in the clinical database for temperature record

**ZOSTER-063 (204928): SOLICITED ADVERSE EVENTS - GENERAL SIGNS/SYMPOTOMS: ONLY TEMPERATURES (Temperatures)**

If there is a temperature that meets the definition of serious, complete an Expedited Adverse Event Report.

**TEMPERATURES**

1.	Temperature (Fahrenheit) collected daily from Day 0 to Day 6  1	[SYMP_VAL_TEMP] [FE_VAL_D0] [FE_VAL_D1] [FE_VAL_D2] [FE_VAL_D3] [FE_VAL_D4] [FE_VAL_D5] [FE_VAL_D6] Day 0: [FE_VAL] Day 1: [FE_VAL] Day 2: [FE_VAL] Day 3: [FE_VAL] Day 4: [FE_VAL_D4] Day 5: [FE_VAL_D5] Day 6: [FE_VAL_D6] XXX.X XXX.X XXX.X XXX.X XXX.X XXX.X XXX.X [FE_NT] [FE_NT] [FE_NT] [FE_NT] [FE_NT] [FE_NT] [FE_NT] Not taken [A:Y] Not taken [A:Y] [A:Y] [A:Y] [A:Y] [A:Y] [A:Y] [A:Y] [A:Y]
2.	Primary route: The preferred route for recording temperature in this study is oral. When there is no other alternative, the temperature may be recorded by other route. [Primary route]	[TEMP_ROUTE] [A:O]  Oral [A:A]  Axillary [A:R]  Rectal [A:T]  Tympanic
3.	Fever first onset time: [Fever 1st onset time]	[FEVER_TM] Req/Unk  : Req/Unk  24-hour clock
4.	Did a temperature above or equal to threshold occur? i.e. during the solicited period at least one axillary/oral/tympanic measure is above or equal to 99.5 °F or at least one rectal measure is above or equal to 100.4 °F  2	[FE_YN] [A:N]  No [A:NT]  Not taken [A:Y]  [FE_ONG] Yes -> After Day 6: Temperature above or equal to threshold? [A:N]  No [A:Y]  [SYMP_ONG_TEMP] [SYMP_MAX_TEMP] Yes -> Max temperature (Fahrenheit): XXX.X [ERDAT] Date of last day of sign/symptom: Req/Unk  / Req/Unk  / Req/Unk  (2016-2018) [CONT_END] Continuing at the end of the study? [A:Y]   [CAUSAL] Is there a reasonable possibility that the AE may have been caused by the investigational product? [A:Y]  Yes [A:N]  No

# Statistical Analysis Plan

GlaxoSmithKline

Study alias & e-track number(s): ZOSTER-063 (204928)

## For temperature

To allow the temperature recording, a separate screen had to be completed whatever the answer to question (2) in [Figure 3](#) and even if no temperature equal or above 37.5°C has been found in the diary card.

All subjects for whom that question (2) in [Figure 3](#) has been answered by “Yes” or “No”, will be included in the summaries of temperature by **half degree (°C) cumulative increments** and classified according to their maximum temperature value observed daily recording over the solicited period. If no daily measurement is recorded for temperature, the subject will not be counted in the summary of subjects with temperature above a specific threshold. For the summary of temperature, the “all” category will not be computed. This table will be produced overall, by route with no route conversion.

## For summary of fever

All subjects for whom that question (2) in [Figure 3](#) has been answered by “Yes” or “No”, will be included in the summaries of fever and classified according to their maximum temperature value observed daily recording over the solicited period even if partial recording. If no daily measurement is recorded for temperature, the subject will not be counted in the summary of subjects with fever and the “all” category will count the number of subject with at least one temperature measurement  $\geq 37.5^{\circ}\text{C} / 99.5^{\circ}\text{F}$  for oral, axillary or tympanic route, or  $\geq 38.0^{\circ}\text{C} / 100.4^{\circ}\text{F}$  for rectal route.

### 7.2.2.3. **Solicited local symptoms**

The analysis of solicited local symptoms will include all subjects for whom the question (1) in [Figure 4](#) about the presence of a solicited local symptoms has been answered by ‘Yes’ or ‘No’(see LOCSOL\_YN item).

The next sections describe how each subject contributes to the analyses, depending on the endpoints.

# Statistical Analysis Plan

Study alias & e-track number(s): ZOSTER-063 (204928)

**Figure 4** Information captured in the clinical database for solicited local symptoms

**ZOSTER-063 (204928): SOLICITED SYMPTOMS (Solicited symptoms)**

**SOLICITED ADVERSE EVENTS - LOCAL SIGNS/SYMPOTMS - REACTOGENICITY TRIGGERED MEDICAL ATTENTION**

1.\* Has the subject experienced any of the Local Solicited signs/symptoms between Day 0 and Day 6?

**1**

[LOCSOL\_YN]  
[A:Y]  Yes -> Please:  
• tick No/Yes for each sign/symptom and complete further as necessary in the "Local signs/symptoms" form,  
• complete the "Reactogenicity triggered medical attention" form.  
[A:N]  No  
[A:U]  Unknown, no information available

---

**ZOSTER-063 (204928): SOLICITED ADVERSE EVENTS - LOCAL SIGNS/SYMPOTMS (HZ/su Vaccine) (Local signs/symptoms)**

If any of these adverse events meets the definition of serious, complete an Expedited Adverse Event Report.

**REDNESS**

1.\* Occurred?

**2**

[RE\_YN]  
[A:N]  No  
[A:Y]  [SYMP\_VAL\_MM]  
Yes -> [SYMP\_VAL\_MM\_D0] [SYMP\_VAL\_MM\_D1] [SYMP\_VAL\_MM\_D2] [SYMP\_VAL\_MM\_D3] [SYMP\_VAL\_MM\_D4] [SYMP\_VAL\_MM\_D5] [SYMP\_VAL\_MM\_D6]  
Size (mm): Day 0:  N5 Day 1:  N5 Day 2:  N5 Day 3:  N5 Day 4:  N5 Day 5:  N5 Day 6:  N5  
[SYMP\_TM]  
Symptom first onset time:  Req/Unk  :  Req/Unk  24-hour clock  
[RE\_ONG]  
After Day 6: Ongoing? [A:N]  No  
[A:Y]  [SYMP\_ONG\_MM]  
Yes -> [SYMP\_MAX\_SIZE]  
Maximum size:  N5  
[ERDAT]  
Date of last day of sign/symptom:  Req/Unk  /  Req/Unk  /  Req/Unk  (2016-2018)  
[CONT\_END]  
Continuing at the end of the study? [A:Y]

# Statistical Analysis Plan

Study alias & e-track number(s): ZOSTER-063 (204928)

For each solicited local symptoms if the answer to (2) in [Figure 4](#) is "No", the subject will be considered as not having that local symptom at the injection site after that dose.

**Subjects who documented the presence of a specific symptom** i.e. if the answer to (2) in [Figure 4](#) is "Yes" (ex RE\_YN=Y), the maximum intensity recording over the considered follow-up period is used for the analysis of the percentage of subjects with symptoms.

**If the subject answered "Yes" to (2) in [Figure 4](#) for a specific symptom BUT partially recorded daily measurement** (e.g., intensity missing for Day 3) over the considered solicited period, s/he will be included in the summaries and classified according to their maximum observed daily recording over the solicited period.

**If the subject answered "Yes" to (2) in [Figure 4](#) for a specific symptom BUT no daily measurement is recorded**, she/he will not be included and counted in the summary of subjects with symptoms above a specified threshold, however s/he will be part of the summary corresponding to the 'All' category.

## 7.2.2.4. Combined Solicited local and general symptoms

The analysis of the combined solicited general and local symptoms will include all vaccinated subjects for whom the question (1) in [Figure 2](#) or [Figure 4](#) about the presence of any solicited general or local symptoms has been answered by 'Yes' or 'No'.

## 7.2.2.5. Unsolicited symptoms

All vaccinated subjects will be considered for the analysis of unsolicited symptoms.

The analysis of unsolicited adverse events, including serious adverse events, consists of evaluating the percentage of subjects with at least 1 report of an unsolicited adverse event classified by the Medical Dictionary for Regulatory Activities (MedDRA).

Subjects who missed reporting unsolicited symptoms will be treated as subjects without unsolicited symptoms.

## 7.2.2.6. Concomitant medication

All vaccinated subjects will be considered for the analysis of concomitant medication use. Subjects who did not report the use of a concomitant medication will be considered as subjects without medication. Subjects will be counted in the summary who started a concomitant medication during the mentioned period and took at least one dose.

# Statistical Analysis Plan

Study alias & e-track number(s): ZOSTER-063 (204928)

## 7.2.2.7. Compliance with respect to documenting safety

The number of doses injected, the number of doses not given according-to-protocol, and the number of symptom sheets (SS) transcribed for local and general symptoms, the compliance for local and general symptoms are tabulated for the Total Vaccinated cohort.

Compliance (%) is defined as the number of general (local) symptom sheets/screens completed divided by the number of doses administered for a specified vaccination (dose) and group.

The number of doses not given according-to-protocol, are the doses injected at the wrong site and/or side, or injected using the wrong route as defined in the study protocol for each study vaccine. This number is issued from the following question in the vaccine administration sheet of the CRF: "Has the study vaccine been administered according-to-protocol?" Study vaccine dose not administered according to protocol can lead to elimination from the ATP cohort, depending to the ATP cohort definition in the protocol.

## 7.2.3. Quality of Life data

At dose 1, if one of the Day -7 or Day 0 pre-vaccination assessments is missing, the baseline value will simply be the non-missing assessment. At dose 2, if 2 or more of the 3 pre-vaccination assessments are missing, the baseline value will be considered missing.

## 7.3. Number of Decimals

The following decimal description from the decision rules will be used for the demography, QoL and safety/reactogenicity analysis.

Display Table	Parameters	Number of decimal digits
Demographic characteristics	Mean, median age	1
Demographic characteristics	SD (age)	2
QoL	SF-36 Components, including LL & UL of CI	2
	EQ-5D Utility Scores, including LL & UL of CI	3
	EQ-5D VAS Scores, including LL & UL of CI	1
	QALY, including LL & UL of CI	3
Reactogenicity	Mean, Min, Q1, Median, Q3, Max for duration	1
All summaries	% of count, including LL & UL of CI	1
All summaries	% of difference, including LL & UL of CI	2

# Statistical Analysis Plan

Study alias & e-track number(s): ZOSTER-063 (204928)

## 8. CONDUCT OF ANALYSES

### 8.1. Sequence of analyses

Two formal analyses are planned: a first analysis and an end of study analysis.

The first analysis will be performed when the reactogenicity and QoL collected from dose 1 up to Visit 3 are available (data as clean as possible). No clinical study report will be written.

The end of study analysis of QoL and safety data will be performed when all data up to the study end (Study conclusion contact) will be available. A clinical study report will be written including all available data and made available to the investigators at that time.

Description	Analysis ID	Disclosure Purpose	Reference for TFL
End of study analysis	E1_01	CTRS, Study report	All tables identified as E1_01 in TFL dated 30MAY2015
Analysis up to Visit 3 Day 7	E1_02	Internal, CTRS	All tables identified as E1_02 in TFL dated 30MAY2015, on data up to Visit 3 Day 7

### 8.2. Statistical considerations for interim analyses

No interim analysis is planned.

## 9. CHANGES FROM PLANNED ANALYSES

- pIMDs will be described in detail. Sub-groups analyses by age stratum and by frailty status have been added.
- Additional analyses of safety have been added following remarks made by CBER on the Zoster-032 study.

# Statistical Analysis Plan

Study alias & e-track number(s): ZOSTER-063 (204928)

# Statistical Analysis Plan

Study alias & e-track number(s): ZOSTER-063 (204928)

## Appendix A DETAILS OF COMPONENTS OF FRAILTY INDEX

Item No	Category	Response		Mapped Score as used in Frailty Index
1	Help Bathing	Yes, No		Yes=1, No=0
2	Help Dressing	Yes, No		Yes=1, No=0
3	Help getting in or out of chair	Yes, No		Yes=1, No=0
4	Help walking in or around house	Yes, No		Yes=1, No=0
5	Help eating	Yes, No		Yes=1, No=0
6	Help Grooming	Yes, No		Yes=1, No=0
7	Help using Toilet	Yes, No		Yes=1, No=0
8	Help up/down stairs	Yes, No		Yes=1, No=0
9	Help lifting	Yes, No		Yes=1, No=0
10	Help shopping	Yes, No		Yes=1, No=0
11	Help with housework	Yes, No		Yes=1, No=0
12	Help with meal preparation	Yes, No		Yes=1, No=0
13	Help taking medications	Yes, No		Yes=1, No=0
14	Help with finances	Yes, No		Yes=1, No=0
15	Cognitive score (MoCA)	Range 0 to 30	Mapped to a score between 0 and 1	If score < 6 then mapped score=1 (Severe Dementia) If 6 <= score <= 11 then mapped score=0.75 (Moderate Dementia) If 12 <= score <= 18 then mapped score=0.5 (Mild Dementia) If 19 <= score <= 25 then mapped score=0.25 (Mild Cognitive impairment) If score >= 26 then mapped score=0 (No Cognitive impairment)

# Statistical Analysis Plan

Study alias & e-track number(s): ZOSTER-063 (204928)

Item No	Category	Response		Mapped Score as used in Frailty Index
16	Self Rating of Health	Poor, Fair, Good, Very Good, Excellent		If rating=Poor then mapped score=1 If rating=Fair then mapped score=0.75 If rating=Good then mapped score=0.5 If rating=Very Good then mapped score=0.25 If rating=Excellent then mapped score=0
17	Health Change in last year	Worse, Better/Same		If change=Worse then mapped score=1 Else mapped score=0
18	Unintentional weight loss	Yes, No		Yes=1, No=0
19	Depression score (CESD-R)	Range 0 to 60	Mapped to a score between 0 and 1	If score < 16 then mapped score=0 If 16 <= score <= 21 then mapped score=0.5 If score > 21 then mapped score=1
20	Weakness (grip strength)	Yes, No		Yes=1, No=0
21	Slow Walking Speed	Yes, No		Yes=1, No=0
22	General Medical History : High Blood pressure,	Yes, No		Yes=1, No=0
23	Heart Attack,	Yes, No		Yes=1, No=0
24	CHF,	Yes, No		Yes=1, No=0
25	Cerebrovascular Disease,	Yes, No		Yes=1, No=0
26	Cancer,	Yes, No		Yes=1, No=0
27	Diabetes Mellitus	Yes, No		Yes=1, No=0
28	Arthritis,	Yes, No		Yes=1, No=0

# Statistical Analysis Plan

Study alias & e-track number(s): ZOSTER-063 (204928)

Item No	Category	Response		Mapped Score as used in Frailty Index
29	Chronic Lung Disease,	Yes, No		Yes=1, No=0
30	Long Term disability or Handicap	Yes, No		Yes=1, No=0
31	Stomach or Intestinal Ulcers	Yes, No		Yes=1, No=0
32	Migraine	Yes, No		Yes=1, No=0
33	Cataract	Yes, No		Yes=1, No=0
34	Hearing Problems	Yes, No		Yes=1, No=0
35	Glaucoma	Yes, No		Yes=1, No=0
36	SF-36 Physical Functioning Score	Derived score for items 3A to 3J. (Range : 0 - 100)		If derived score =0 then mapped score=0 If derived score = 50 then mapped score=0.5 If derived score =100 then mapped score=1

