### 6.2.1. SF-36 and EQ-5D

The SF-36 health survey and the EQ-5D questionnaires will be completed by all subjects at each study visits (i.e., Visit 1 Day -7, Visit 2 Month 0 (before the vaccination), Visit 3 Day 7, Visit 4 Month 2 (before the vaccination) and Visit 5 Day 67). Additionally, after each vaccination, the subjects will be given the questionnaires to take home and asked to complete only questions 3a through 3j of the SF-36 questionnaires and the entire EQ-5D questionnaires, on a daily basis on Days 1 to 6 post-vaccination.

Each of the 8 components of the SF-36 Questionnaire and the EQ-5D Utility and VAS scores will be presented at each scheduled visit (Day -7, Day 0, Day 7, Day 60 and Day 67) including the derived baseline values for each dose. In addition the SF-36 physical functioning score (PF) (based on questions 3a to 3j) and the EQ-5D utility and VAS scores will be presented on days 1 to 6 following each dose. Further details of the SF-36 components and EQ-5D Utility and VAS scores can be found in section [7.1.3](#).

The primary endpoint variable is the SF-36 Physical Functioning (PF) scale. The analysis will be performed on the subgroups detailed in [Table 1](#).

The 10 individual questions that form the SF-36 PF scale will be analysed on an individual basis. The three responses (Limited a lot, Limited a little, Not limited at all) to the individual questions will be assigned a score of 0, 50, or 100. In this way a baseline score and a mean score over the 7 days post each dose can be calculated for each individual question. Summary statistics of the change from baseline will be presented for each individual question.

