## 6.2.2. EQ-5D Utility / Quality adjusted life years (QALY)

The calculation of the baseline and post baseline values for the analysis of QALY loss is detailed in section [7.1.3](#).

The 95% CI for Quality-adjusted life year (QALY) mean loss will be obtained using a multiple regression model on the change from baseline EQ-5D utility scores. The model will include age strata, gender and frailty status as the fixed effect.

The 95% CI for utility scores will be obtained pre- and post-vaccination separately assuming that utility scores were normally distributed with unknown variance.

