## 6.3. Frailty Status

An assessment of frailty status will be done at Visit 1. Frailty status will be measured in relation to the accumulation of deficits using a frailty index (FI) calculated according to the model proposed by Mitnitski et al. [Mitnitski, 2001]. The different aspects of frailty composing the FI will be assessed through a series of certified tests and specific questions in the following domains:

- Cognition: a 30-point questionnaire that is used extensively in clinical and research settings to measure cognitive impairment called the Montreal Cognitive Assessment (MoCA);
- Physical status: criteria for the definition of frailty developed by Fried et al. [Fried, 2001] to categorize the physical frailty phenotype (PFP), the physical functioning category of the SF-36 questionnaire will be used as measure of the physical activity of the subject [Ryb, 2012];
- Depression and exhaustion: a screening test for depression and depressive disorder called the Center for Epidemiologic Studies Depression Scale – Revised (CESD-R);
- Multimorbidity: occurrence of a specific age dependent list of diseases based on the published work [Mitnitski, 2001]. The 14 medical history items are : High Blood Pressure, Heart Attack, CHF, Cerebrovascular disease, Cancer, Diabetes Mellitus, Arthritis, Chronic Lung Disease, Long Term Disability or Handicap, Stomach or Intestinal Ulcers, Migraine, Cataract, Hearing Problems and Glaucoma.
- Disability: assessment of the subjects' dependence on others to perform a list of specific daily activities (based on the published work [Mitnitski, 2001; **Error! Reference source not found.**, 2008]).

The range of the index is 0 to 36. The contribution of each component is as follows:

Category	Range
Medical History	0 – 14
Disability assessment	0 – 14
CESD-R depression scale	0 – 1
SF-36 PF score	0 – 1
Cognitive assessment (MoCA)	0 – 1
Unintentional weight loss	0 – 1
Weakness (grip strength)	0 – 1
Slow walking speed	0 – 1
Self-rating of health	0 – 1
Health change in last year	0 – 1
Total	0 – 36

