# Statistical Analysis Plan

Study alias & e-track number(s): ZOSTER-063 (204928)

Each subject will be assigned to one of three categories, Non-Frail, Pre-Frail and Frail.

If the score is  $\leq 3$  then the subject is classified as Non-Frail. If the score is greater than 3 but less than or equal to 8 then the subject is classified as pre-frail. If the score is greater than 8 then the subject is classified as Frail.

A subject must have at least 30 non-missing components in order to be assigned a frailty index classification. However in the event that a subject with a partially completed frailty assessment has a score greater than 8 then the classification will be Frail even if the total number of completed responses is less than 30.

Further details of the Frailty index components can be found in [Appendix A](#)

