## 7.1.3. Quality of Life data

### 7.1.3.1. Calculation of study day for SF-36 and EQ-5D Assessments

Each EQ-5D and SF-36 assessment at a scheduled time point will be re-classified into time points based on the date of assessment relative to date of vaccination:

Studyday=date of assessment – date of vaccination.

To be considered evaluable at day 0 a questionnaire must have been filled in within 14 days of vaccination date. Questionnaires without a date of assessment were to be considered not evaluable. In case of two questionnaires with the same date of assessment the minimum value (i.e. the value which represents worst quality of life) of the two assessments will be selected as evaluable.

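### Frailty index item 36 scores SF-36 Physical Functioning in the wrong direction and gives no score for 18 of its 21 possible values

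*SAP*

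**What the plan says.** SAP section 6.3 sets the direction of the index: "Frailty status will be measured in relation to the accumulation of deficits using a frailty index (FI"). The total runs from 0 to 36. Totals up to 3 are Non-Frail and totals above 3 up to 8 are Pre-Frail; at the top, "If the score is greater than 8 then the subject is classified as Frail". On incomplete assessments, "A subject must have at least 30 non-missing components in order to be assigned a frailty index classification", except that a partial score above 8 is still Frail.

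Appendix A lists the 36 items. The worse state gets the higher score throughout items 1 to 35. For self-rated health (item 16), for example, "If rating=Poor then mapped score=1". The last item, SF-36 PF with derived range 0 to 100, is scored: "If derived score =0 then mapped score=0 If derived score = 50 then mapped score=0.5 If derived score =100 then mapped score=1".

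Two other places fix the direction of PF. In section 6.2.1 the responses ("Limited a lot, Limited a little, Not limited at all) to the individual questions will be assigned a score of 0, 50, or 100". Section 7.1.3.1, on duplicate questionnaires, selects "the minimum value (i.e. the value which represents worst quality of life").

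Frailty class is then used in the QALY regression (section 6.2.2): "The model will include age strata, gender and frailty status as the fixed effect". The model code in section 7.1.3.4 requests least-squares means and pairwise differences by frailty. Frailty class also splits the demographic tables (6.1) and safety analyses (6.6), and it is a Table 1 subgroup for the PF analysis (6.2.1).

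**The concern.** There are two defects. The first is direction: in an index that counts deficits, item 36 counts good physical function as a deficit. The second is coverage: the item has a score only at PF 0, 50 and 100, so at any other value the programmer must choose an unstated rule.

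The protocol assesses frailty to characterise the population and to see whether it influences reactogenicity and, through that, quality of life (section 1.2.2). If the class is wrong near the cut-offs, the frailty rows of the QALY, PF and safety tables compare groups that are not what their labels say. The misclassification is also systematic. Item 36 uses PF measured before vaccination, and PF is the variable of the primary endpoint, so errors in class are tied to starting PF in the very subgroup tables that report PF change.

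**Working it through.** **Index range.** 14 medical history items + 14 disability items + 8 single components = 36. This reproduces the stated range of 0 to 36 and matches the 36 rows of Appendix A.

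**Direction.** The closest comparison is item 15, the MoCA cognitive score, which is also a scale where higher is better.

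| Item | Best state scores | Worst state scores |
|---|---|---|
| 15, MoCA | 26 or more → 0 | below 6 → 1 |
| 16, self-rated health | Excellent → 0 | Poor → 1 |
| 36, PF | 100 → 1 | 0 → 0 |

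The SAP reverses MoCA and does not reverse PF. No other section reverses it. The 0–1 range given for the PF component in section 6.3 sets no direction.

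**Coverage.** Ten items scored 0, 50 or 100 and averaged give PF = 5s for s = 0, 1, …, 20, which is 21 values. Three are scored, so 21 − 3 = 18 are not. MoCA and the CESD-R depression scale, by contrast, have complete bands.

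**Size of the error.** Take 1 − PF/100 as the corrected score (an assumption; the SAP states no such rule).
- PF 100: written 1, corrected 0, error +1.
- PF 50: written 0.5, corrected 0.5, error 0.
- PF 0: written 0, corrected 1, error −1.

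**Effect on class.** Let T be the total of the other 35 items, which moves in steps of 0.25. Each value of T was classified with the written and the corrected score. At unlisted PF values two readings were tried: the item adds 0, or it is interpolated as PF/100, the line through the three stated points. The table gives the values of T at which the class is wrong around cut-off 3; add 5 for cut-off 8.

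| PF | Unlisted values add 0 | Unlisted values interpolated |
|---|---|---|
| 0 (listed) | too low, 2.25–3.00 | same |
| 5–20 | too low, 2.25–3.00 | too low, 2.25–2.75 |
| 25 | too low, 2.50–3.00 | too low, 2.50–2.75 |
| 30–45 | too low, 2.50–3.00 | too low, 2.50 |
| 50 (listed) | none | none |
| 55–70 | too low, 2.75–3.00 | too high, 2.50 |
| 75 | too low, 3.00 | too high, 2.50–2.75 |
| 80–95 | too low, 3.00 | too high, 2.25–2.75 |
| 100 (listed) | too high, 2.25–3.00 | same |

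The two readings disagree with each other for some T at all 18 unlisted values. A third reading, treating the item as missing, adds nothing to the total, like zero. It differs for a subject with exactly 29 of the other 35 items present, who then falls below the 30-component minimum and is unclassified unless the partial score exceeds 8.

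**An ordinary case.** High blood pressure (1) + arthritis (1) + self-rated health Good (0.5) gives T = 2.5. With PF 100 the written rule gives 2.5 + 1 = 3.5, Pre-Frail. Corrected, it gives 2.5 + 0 = 2.5, Non-Frail.

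**How common the PF values may be (illustration only).** Protocol section 10.3 gives a baseline PF mean of 81.8 and SD of 18.45, taken from another trial. Four assumed distribution shapes matched to these figures put 20% to 31% of subjects at PF 100, 66% to 78% at an unlisted value, 5% to 7% at PF 5–45, and about 0.1% or less at PF 0. These are shares of subjects at each PF value, not shares misclassified.

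**The case against.** The case on the other side concerns weight rather than substance.

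- **The documents show a written rule, not the program.** The code may already be right. This stands: the effect on outputs is conditional on programming as written. But the SAP is the specification that the code is checked against, and its text cannot be implemented without an unstated choice.
- **The three points may be shorthand for a linear map.** They do lie on PF/100. That is plausible but not stated, and it would settle coverage only, because a linear map through those points is still reversed.
- **The error bands depend on the comparator.** This stands for PF 5–95. If the corrected rule used bands with, say, PF 75–100 scoring 0, the adds-0 reading would give no error there. Only the endpoints, PF 100 too high and PF 0 too low, hold under either style of correction.
- **The impact is bounded.** The item moves a 36-point index by at most 1 point. The overall primary estimate does not use frailty, no objective is broken down by it, the protocol makes its frailty sub-analysis conditional on the data (section 10.6.2), and the analyses are descriptive (section 10.7). Help with walking, stairs and lifting, grip strength and walking speed still capture physical function in the right direction. All of this stands, and it limits the severity. Descriptive subgroup tables still need correctly defined subgroups.

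**Conclusion.** The concern holds. Item 36 contradicts the SAP's own PF scoring and the direction of the other 35 items, and it leaves 18 of 21 complete-scale PF values without a score.

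If it is programmed as written, subjects with PF 100 are one class too frail when the other items total 2.25–3.00 or 7.25–8.00, whatever is done at unlisted values. The upper window is probably rare in someone with no limitation in any activity. Measured against 1 − PF/100, subjects with PF below 50 are classed too robust near a cut-off, whether unlisted values add 0 or are interpolated; the missing-item reading adds only the unclassified exception. For PF 55–95 the direction of the error depends on the reading.

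The number of subjects reclassified cannot be derived, because the documents do not give the joint distribution of PF and the other items. The point should be fixed before the frailty outputs are produced or relied on, but it does not threaten the primary result.

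**What to change.** Replace the scoring line of item 36 with a reversed rule that covers every PF value from 0 to 100. Either of these would do:

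- mapped score = 1 − PF/100; or
- complete bands, as for MoCA and CESD-R, with PF 100 scoring 0 and the lowest band scoring 1.

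State also that the item counts as missing only when the PF scale score itself is missing, so that the 30-component rule is unambiguous. Then check the derivation program against the corrected line, and confirm that the cut-offs of 3 and 8 were meant for an index with this item scored as a deficit. If frailty outputs have already been run with the written rule, re-derive the class and rerun them.

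The cost is one line in the appendix, one line of code and the two checks. The PF items are already collected at Visit 1, so no new data are needed.
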